6.3.3 Effective contraception for female volunteers of childbearing potential

Female volunteers are required to use an effective form of contraception during the course of the study, for at least 3 months after their final vaccination procedure. As this is a Phase I, 'first-in-human, study there is no information about the effect of this vaccine on a foetus. Male subjects with female partners of child-bearing potential are not required to use barrier methods for the purposes of contraception whilst taking part in this study as the risk of excretion of the vaccine is negligible.

Acceptable forms of contraception for female volunteers include:

- Established use of oral, injected or implanted hormonal methods of contraception.
- Placement of an intrauterine device (IUD) or intrauterine system (IUS).
- Barrier methods of contraception (condom or occlusive cap with spermicide)
- Male sterilisation, if the vasectomised partner is the sole partner for the subject.
- True abstinence: when this is in line with the preferred and usual lifestyle of the subject. Periodic abstinence (e.g. calendar, ovulation, symptothermal, post-ovulation methods), declaration of abstinence for the duration of exposure to IMP, and withdrawal are not acceptable methods of contraception

Under this protocol, a woman is considered of childbearing potential (WOCBP), i.e. fertile, following menarche and until becoming post-menopausal unless permanently sterile. Permanent sterilisation methods include hysterectomy, bilateral salpingectomy and

bilateral oophorectomy. A postmenopausal state is defined as no menses for 12 months without an alternative medical cause.

6.3.4 Prevention of 'Over Volunteering'

Volunteers will be excluded from the study if they are concurrently involved in another trial. In order to check this, volunteers will be asked to provide their National Insurance or Passport number (if they are not entitled to a NI number) and will be registered on a national database of participants in clinical trials (www.tops.org.uk).

6.3.5 Criteria for postponement of vaccination

The following events constitute contraindications to administration of the vaccine at that point in time; if any one of these events occurs at the time scheduled for vaccination, the subject may instead be vaccinated at a later date following resolution and within the window of screening procedures (defined in section 7.4.1), or withdrawn at the discretion of the Investigator.

- Acute disease at the time of vaccination. Acute disease is defined as the presence of a moderate or severe illness with or without fever.
- Temperature of >37.5°C (99.5°F) at the time of vaccination.

6.3.6 Withdrawal of Volunteers

In accordance with the principles of the current revision of the Declaration of Helsinki and any other applicable regulations, a volunteer has the right to withdraw from the study at any time and for any reason, and is not obliged to give his or her reasons for doing so. The Investigator may withdraw the volunteer at any time in the interests of the volunteer's health and well-being. In addition the volunteer may withdraw/be withdrawn for any of the following reasons:

- Administrative decision by the Investigator.
- Ineligibility (either arising during the study or retrospectively, having been overlooked at screening).
- Significant protocol deviation.
- Volunteer non-compliance with study requirements.
- An AE, which requires discontinuation of the study involvement or results in inability to continue to comply with study procedures.

The reason for withdrawal will be recorded in the CRF. If withdrawal is due to an AE, appropriate follow-up visits or medical care will be arranged, with the agreement of the volunteer, until the AE has resolved, stabilised or a non-trial related causality has been assigned. Any volunteer who is withdrawn from the study may be replaced, if that is possible

within the specified time frame. The Local Safety Monitor (LSM) may recommend withdrawal of volunteers.

Any volunteer who fails to attend for two or more follow-up visits during the study will be deemed to have withdrawn from the study.

If a volunteer withdraws from the study, blood samples collected before their withdrawal from the trial will be used/ stored unless the volunteer specifically requests otherwise.

In all cases of subject withdrawal, excepting those of complete consent withdrawal, long-term safety data collection, including some procedures such as safety bloods, will continue as appropriate if subjects have received one or more vaccine doses.

6.4 Compliance with Dosing Regime

All doses in this vaccine study will be administered by the Investigator and recorded in the CRF. The study medication will be at no time in the possession of the volunteer and compliance will, therefore, not be an issue.

6.5 Pregnancy

Should a volunteer become pregnant during the trial, she will be followed up as other volunteers and in addition will be followed until pregnancy outcome. We will not routinely perform venepuncture in a pregnant volunteer.

7. CLINICAL PROCEDURES

This section describes the clinical procedures for evaluating study participants and follow-up after administration of study vaccine.

7.1 Study procedures

All volunteers will have the same schedule of clinic attendances and procedures as indicated in the schedules of attendance (Table 5). All subjects will receive the ChAdOx1 RVF vaccine, and undergo follow-up for a total of 12 weeks. The total volume of blood donated during the study will be 300mL. Additional visits or procedures may be performed at the discretion of the investigators, e.g., further medical history and physical examination, urine microscopy in the event of positive urinalysis or additional blood tests if clinically relevant.

7.2 Observations

Pulse, blood pressure and temperature will be measured at the time-points indicated in the schedule of procedures and may also be measured as part of a physical examination if indicated at other time-points.

7.3 Blood Tests and Urinalysis

Blood will be drawn for the following laboratory tests and processed:

1. At Oxford University Hospitals' NHS Trust using NHS standard procedures:
 - **Haematology;** Full Blood Count
 - **Biochemistry;** Sodium, Potassium, Urea, Creatinine, Albumin, Liver Function Tests (ALT, ALP, Bilirubin)
 - **Diagnostic serology;** HBsAg, HCV antibodies, HIV antibodies (specific consent will be gained prior to testing blood for these blood-borne viruses)
 - **Immunology;** Human Leukocyte Antigen (HLA) typing

Additional safety blood tests may be performed if clinically relevant at the discretion of the medically qualified investigators. These generally include, but are not limited to AST, GGT and a coagulation screen.

2. At University of Oxford research laboratories:
 - **Exploratory Immunology;** Immunogenicity will be assessed by a variety of immunological assays. These may include antibodies to Gn and Gc proteins by ELISA and virus neutralising assays, ex vivo ELISpot assays for interferon gamma and flow cytometry assays, functional antibody assays and B cell analyses. Other exploratory immunological assays including cytokine analysis and other antibody assays, DNA

analysis of genetic polymorphisms potentially relevant to vaccine immunogenicity and gene expression studies amongst others may be performed at the discretion of the Investigators.

3. **Urinalysis;** Urine will be tested for protein, blood and glucose at screening. For female volunteers only, urine will be tested for beta-human chorionic gonadotrophin (β -HCG) at screening and immediately prior to each vaccination.

Collaboration with other specialist laboratories in the UK, Europe and outside of Europe for further exploratory immunological tests may occur. This would involve the transfer of serum or plasma and/or PBMC to these laboratories, but these would remain anonymised. Volunteers will be asked for their consent for this before enrollment. Immunological assays will be conducted according to local SOPs.

Subjects will be informed that there may be leftover samples of their blood (after all testing for this study is completed), and that such samples may be stored indefinitely in the Oxford Vaccine Center Biobank for possible future research (exploratory immunology), including human DNA and RNA analyses to search for correlates of vaccine immunogenicity and efficacy. Subjects will be able to decide if they will permit such future use of any leftover samples. If a subject elects not to permit this, all of that subject's leftover samples will be discarded after the required period of storage to meet Good Clinical Practice (GCP) and regulatory requirements. Urine samples will be destroyed after analysis and will not be stored for future research use.

7.4 Study visits

The study visits and procedures will be undertaken by one of the clinical trials team. The procedures to be included in each visit are documented in the schedule of attendances (Table 5). Each visit is assigned a time-point and a window period, within which the visit will be conducted.

7.4.1 Screening visit

All potential volunteers will have a screening visit, which may take place up to 90 days prior to vaccination. Informed consent will be taken before screening, as described in section 6.2. If consent is obtained, the screening procedures indicated in the schedule of attendances will be undertaken. To avoid unnecessary additional venepuncture, if the appropriate blood test results for screening are available for the same volunteer from a screening visit for another Jenner Institute Clinical Trials group vaccine study, these results may be used for assessing eligibility (provided the results date is within the 3 months preceding enrolment in RVF001).

The subject's general practitioner will be contacted with the written permission of the subject after satisfactory screening as notification that the subject has volunteered for the study and to ascertain any significant medical history. During the screening the volunteers will be asked to provide their National Insurance or passport number so that this can be entered on to a national database which helps prevent volunteers from participating in more than one clinical trial simultaneously or over-volunteering for clinical trials (www.tops.org.uk).

Abnormal clinical findings from the urinalysis or blood tests at screening will be assessed by the lead clinician according to the relevant SOP. Abnormal blood tests following screening will be assessed according to site-specific laboratory adverse event grading tables which are filed in the trial master file (TMF) or the Investigator Site File (ISF). Any abnormal test result deemed clinically significant may be repeated to ensure it is not a single occurrence. If an abnormal finding is deemed to be clinically significant, the volunteer will be informed and appropriate medical care arranged with the permission of the volunteer.

The eligibility of the volunteer will be reviewed by the study clinician at the end of the screening visit and again when all results from the screening visit have been considered. Decisions to exclude the volunteer from enrolling in the trial or to withdraw a volunteer from the trial will be at the discretion of the Investigator. If eligible, a day 0 visit will be scheduled for the volunteer to receive the vaccine.

7.4.2 Day 0: Enrolment and Vaccination Visit

Volunteers will not be considered enrolled in the study until they have received a vaccine. Before vaccination, the eligibility of the volunteer will be reviewed including re-checking informed consent and willingness to be vaccinated. Pulse, blood pressure and temperature will be observed and if necessary, a medical history and physical examination may be undertaken to determine need to postpone vaccination depending on criteria listed in section 6.3.5. Vaccinations will be administered as described below.

7.4.2.1 Vaccinations

Before each vaccination, the on-going eligibility of the volunteer will be reviewed. All vaccines will be administered intramuscularly according to SOP VC002 Vaccination as described below in section 8.4 and the vaccine dilution SOP when required. The injection site will be covered with a sterile dressing and the volunteer will stay in the CCVTM for observation, in case of immediate adverse events. Observations will be taken 30 minutes after vaccination (+/- 5 minutes) and the sterile dressing removed and injection site inspected. Observations will also be taken at 60 minutes (+/- 10 minutes) before the volunteer leaves. An oral thermometer, tape measure and diary card (paper or electronic) will be given to each volunteer, with instructions on use, along with the emergency 24 hour telephone number to contact the on-call study physician if needed.

Diary cards will collect information on the timing and severity of the following solicited AEs:

Table 3. Solicited AEs as collected on post vaccination diary cards

Local solicited AEs	Systemic solicited AEs
Pain	Fever
Redness	Feverishness
Warmth	Joint pains
Itch	Muscle pains
	Fatigue
	Headache
	Nausea
	Malaise

Volunteers will be instructed on how to self-assess the severity of these AEs. There will also be space on the diary card to self-document unsolicited AEs, and whether medication was taken to relieve the symptoms.

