4.1.1 Primary Outcome Measures

The specific endpoints for safety and reactogenicity will be actively and passively collected data on adverse events.

The following parameters will be assessed for all study groups

- Occurrence of solicited local reactogenicity signs and symptoms for 7 days following the vaccination
- Occurrence of solicited systemic reactogenicity signs and symptoms for 7 days following the vaccination
- Occurrence of unsolicited adverse events for 28 days following the vaccination
- Change from baseline for safety laboratory measures
- Occurrence of serious adverse events during the whole study duration

Volunteers will undergo clinical follow up for a further 90 days following completion of the vaccination regimen. SAEs will be collected throughout the study. The duration of follow up reflects the desire to obtain safety data with the first use of ChAdOx1 RVF in humans.

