7.4.4 COVID-19 Study Considerations

The study will be carried out in line with the latest Public Health England (PHE) advice. Local SOPs for the use of appropriate personal protective equipment (PPE) and social distancing will be followed by clinical staff.

Participants must consent to inform the trial team of covid-19 infection during the study as part of the informed consent process, in order to be enrolled in the study. Participants will be reminded to follow the up to date local public health guidance regarding COVID-19 during the trial. Inkeeping with PHE guidance on vaccine associated fever during the pandemic (75), participants experiencing fever within the first 48 hours of vaccination, with no other primary symptom of covid-19 (cough, anosmia, ageusia) will not be required to self-isolate unless there is otherwise clinical suspicion of COVID-19.

Participants will be able to discuss symptoms with a medically qualified oncall study clinician via mobile phone at all times during the study. Participants describing potential COVID-19 symptoms may be recommend to seek follow up and testing for COVID-19 through healthcare pathways available to them.

Table 5. Schedule of attendances

Attendance Number	1 ^S	2	3	4	5	6	7	8
Timeline** (days)	≤ 90	0	2	7	14	28	56	84
Time window (days)			±1	±2	±3	±3	±7	±7
Informed Consent	X							
Review contraindications, inclusion and exclusion criteria	X	X						
Vaccination		X						
Vital signs [^]	X	X	X	X	X	X	X	X
Ascertainment of adverse events		X	X	X	X	X	X	X
Diary cards provided		X						
Diary cards collected						X		
Medical History, Physical Examination	X	(X)	(X)	(X)	(X)	(X)	(X)	(X)
Biochemistry [§] , Haematology (mL)	5	5	5	5		5		
Exploratory immunology [£] (mL)		50		10	50	50	50	50
Urinalysis	X							
Urinary β–HCG (women only)	X	X						
HLA typing (mL)		4						
HBsAg, HCV Ab, HIV serology (mL)	5							
Blood volume per visit	10	59	5	15	50	55	50	50
Cumulative blood volume [%]	10	69	74	89	139	194	244	294

S = screening visit; (X) = if considered necessary ^ = Vital signs includes pulse, blood pressure and temperature; § = Biochemistry will include Sodium, Potassium, Urea, Creatinine, Albumin and Liver function tests. £ = Exploratory immunology includes antibodies to RVFV, ex vivo interferon-gamma ELISpot responses to RVFV

** Timeline is approximate only. Exact timings of visits relate to the day on enrolment, ie, each visit must occur at indicated number of days after enrolment ± time window.

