9.1.6 Suspected Unexpected Serious Adverse Reaction (SUSAR)

A serious adverse reaction, the nature and severity of which is not consistent with the information about the medicinal product in question set out in the IB or Summary of Product Characteristics (SmPC).

9.2 Foreseeable Adverse Reactions:

The foreseeable ARs following vaccination with ChAdOx1 RVF include injection site pain, erythema, warmth, swelling, pruritus, myalgia, arthralgia, headache, fatigue, fever, feverishness, malaise and nausea.

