9.6 Assessment of severity

The severity of clinical and laboratory adverse events will be assessed according to the scales in Tables 6-8, also described in the SOP VC027.

Table 7. Severity grading criteria for local adverse events.

Adverse Event	Grade	Intensity
Erythema at injection site*	1	>3 - ≤50 mm
	2	>50 - ≤100 mm
	3	>100 mm
Swelling at injection site	1	>3 - ≤20 mm
	2	>20 - ≤50 mm
	3	>50 mm
Ulceration/necrosis of skin at injection site	1	-
	2	-
	3	Any

*erythema or swelling ≤3mm is an expected consequence of skin puncture and will therefore not be considered an adverse event.

Table 8. Severity grading criteria for physical observations

	Grade 1 (mild)	Grade 2 (moderate)	Grade 3 (severe)
Fever (oral)	37.6°C - 38.0°C	38.1°C – 39.0°C	>39.0°C
Tachycardia (bpm)*	101 - 115	116 – 130	>130
Bradycardia (bpm)**	50 – 54	40 – 49	<40
Systolic hypertension (mmHg)	141 - 159	160 – 179	≥180
Systolic hypotension (mmHg)***	85 - 89	80 – 84	<80
Diastolic hypertension (mmHg)	91 - 99	100 – 109	≥110

*Taken after ≥10 minutes at rest

**Use clinical judgement when characterising bradycardia among some healthy subject populations, for example, conditioned athletes.

***Only if symptomatic (e.g. dizzy/ light-headed)

Table 9. Severity grading criteria for local and systemic AEs.

GRADE 0	None: Symptom not experienced
GRADE 1	Mild: Short-lived or mild symptoms; medication may be required. No limitation to usual activity
GRADE 2	Moderate: Mild to moderate limitation in usual activity. Medication may be required.
GRADE 3	Severe: Considerable limitation in activity. Medication or medical attention required.

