9.9 Safety Stopping/Holding Rules

Safety holding rules have been developed considering the fact that this is a first-in-human dose escalation study.

‘Solicited adverse events’ are those listed as foreseeable adverse events in section 9.2 of the protocol, occurring within the first 7 days after vaccination (day of vaccination and six subsequent days). ‘Unsolicited adverse events’ are adverse events other than the foreseeable AEs occurring within the first 7 days, or any AEs occurring after the first 7 days after vaccination.

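### Sections 9.2 and 9.9 make injection-site swelling a solicited reaction, but the diary list in Table 3 omits it, so it is liable to be under-recorded in the primary local reactogenicity outcome

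*Protocol*

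**What the plan says.** Two parts of the protocol list the solicited adverse events.

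- **Diary list.** Section 7.4.2.1: "Diary cards will collect information on the timing and severity of the following solicited AEs". Table 3 follows, with pain, redness, warmth and itch as local items and eight systemic items. The same section adds: "There will also be space on the diary card to self-document unsolicited AEs".
- **Definition.** Section 9.9 says solicited events "are those listed as foreseeable adverse events in section 9.2 of the protocol, occurring within the first 7 days after vaccination", and counts the day of vaccination and the six days after it. The section 9.2 list is "injection site pain, erythema, warmth, swelling, pruritus, myalgia, arthralgia, headache, fatigue, fever, feverishness, malaise and nausea".

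Swelling is treated as an expected reaction elsewhere too. Section 5.3 names it among the expected local effects, and Table 7 in section 9.6 has its own row, "Swelling at injection site", graded by diameter.

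Two parts of the plan depend on the list. The first primary outcome in section 4.1.1 is "Occurrence of solicited local reactogenicity signs and symptoms for 7 days following the vaccination". In section 9.9.1, the solicited-local holding rule is met when 2 or more participants have a grade 3 solicited local event starting on the day of vaccination or the day after.

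**The concern.** The two lists should be the same and are not. As written, volunteers are prompted for every solicited reaction except swelling, although swelling is one of only two local signs that Table 7 grades over three size bands. An event that must be measured, and that may peak and fade between visits, depends most on a prompt.

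Two things are at stake. First, the frequency, peak size, onset and duration of swelling are liable to be under-recorded relative to the other local reactions in a primary safety outcome. Section 10 says safety data will be presented by frequency, severity and duration. Data that were never collected cannot be restored by any later analysis plan.

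Second, the only place on the card for a volunteer to write swelling is the space for unsolicited events. It could then be handled under the unsolicited holding rule, which requires at least possible relatedness, instead of the solicited-local rule, which does not.

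**Working it through.** **1. Match the two lists.**

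| Section 9.2 | Table 3 |
|---|---|
| pain | pain |
| erythema | redness |
| warmth | warmth |
| pruritus | itch |
| **swelling** | **none** |
| myalgia | muscle pains |
| arthralgia | joint pains |
| headache, fatigue, fever, feverishness, malaise, nausea | the same six |

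Section 9.2 has 5 local + 8 systemic = 13 terms. Table 3 has 4 local + 8 systemic = 12. All 12 match one to one, and swelling is the only unmatched term in either direction. Coverage is 12/13 overall and 4/5 for local reactions.

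**2. Could the redness item stand in?** No. In Table 7, swelling is grade 3 above 50 mm and erythema only above 100 mm. A 60 mm swelling is grade 3, while a 60 mm redness is grade 2.

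**3. What else would capture swelling?**

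- Adverse events are ascertained at every visit from day 0 (Table 5), and section 7.4.3 includes assessment of local events and diary review.
- Section 9.5 requires recording of all local events observed or reported over 28 days.
- Volunteers have free text on the card, a 24-hour telephone number and a tape measure.
- On day 0, 30 minutes after vaccination, the protocol schedules "the sterile dressing removed and injection site inspected". This is the only expressly scheduled inspection of the site. Section 7.4.3 ties physical examination to the schedule, and after screening Table 5 leaves it to be done only where thought necessary.

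**4. Clinic contact inside the solicited window (days 0 to 6, 7 days).**

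- Nominal visits: day 0 and day 2, so 2 of 7 days, leaving 7 − 2 = 5 without contact.
- The day 7 visit has a window of ±2 days. Held on day 5 or 6, it gives 3 of 7, leaving 4.
- The day 2 visit is at 48 h ± 24 h, that is 24 to 72 h. If it is held at 24 h, the holding rule's onset window (to the end of day 1) is still open, and the next scheduled visit is on day 7 − 2 = day 5 at the earliest.

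**5. Effect on the holding rules.** Suppose two participants each have a grade 3 local event starting on day 0 or 1, one of them swelling.

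- Filed as section 9.9 defines: solicited-local count = 2, rule met.
- Swelling missed: solicited-local count = 1, rule not met.
- Swelling filed as unsolicited, with no other grade 3 unsolicited event: solicited-local count = 1, unsolicited count at most 1, neither rule met.

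The result changes only if the swelling starts on day 0 or 1 and is needed to reach 2.

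**6. Size.** The protocol gives neither a swelling rate nor a capture rate. If unprompted reporting captures a fraction c of swelling, and prompted reporting is taken as complete, the relative under-count is 1 − c. For an assumed c of 0.5 to 0.9 this is 0.5 to 0.1, or 50% to 10%. One missed participant moves the observed proportion by 1/3 (33 percentage points) in Group 1 and by 1/6 (17 points) in Groups 2 and 3.

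**The case against.** The strongest reply accepts the mismatch and disputes its consequence.

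- **The protocol never says diary entries are daily,** and the card and the SOP it refers to are not shown. This stands as a limit: the point concerns Table 3 as written. But the text does say the card collects timing and severity of the listed items, and swelling is not among them.
- **Clinic capture is substantial.** Ascertainment is mandatory at each visit, and a day 7 visit held after the window closes still covers the whole week by recall. This is true and reduces the loss. It may establish that swelling occurred; it is a weaker source for peak diameter, onset and duration.
- **A misfiled event stays in the primary safety data,** because unsolicited events over 28 days are also a primary outcome. This is correct, so misfiling changes the category and does not remove the event. It would still make the solicited local results incomplete.
- **The holding-rule contrast is narrow.** Section 9.9 classifies by type and timing, so filing early swelling as unsolicited would already breach the text. Under Table 6, swelling at the injection site soon after vaccination would very probably be at least possibly related. The unsolicited rule also has no two-day onset limit. In addition, dose escalation waits for a review by the Local Safety Monitor, and the study can be held for any single event. All of this stands, and the holding-rule effect is a secondary argument.
- **No conclusion is shown to change.** The safety reporting is descriptive and the 10–50% range is an assumption. That is fair. Whether a volunteer had any local reaction would change only if swelling was the sole one.

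**Conclusion.** The point holds and should be fixed. Table 3 contradicts section 9.2 read with section 9.9: swelling is the one solicited reaction of 13, and the one local reaction of 5, without a diary item. The existing safeguards make the likely effect partial under-recording or misclassification, not total loss. The extent cannot be derived from the documents; 10–50% in relative terms is only what an assumed unprompted capture of 50–90% would imply. Missed or misfiled grade 3 swelling can, but need not, decide whether the solicited-local holding rule is met.

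The conclusion rests on Table 3 being complete as read. A row lost in extraction cannot be wholly excluded, but the one-to-one match of the other 12 terms gives no sign of one.

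**What to change.** Reconcile Table 3 with sections 9.2 and 9.9:

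1. Add a local row for swelling to Table 3 and to the diary card, recording the largest diameter in mm and the onset date, graded by Table 7.
2. State in section 7.4.2.1 that any section 9.2 reaction entered in the free-text space within the first 7 days is filed as solicited, as section 9.9 already defines.

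The cost is one diary row and a wording amendment. No visit or equipment is added, since each volunteer already receives a tape measure, and no holding threshold, dose or clinical rule changes. The row has to be in place before the diaries are used, because the measurements cannot be recovered afterwards.
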